5.5 Study Evaluations

5.5A. Quantitative Data Collection (Aim 1, Aim 2, Exploratory Aim).

Except where indicated, data collection for the IC and RCT phase is identical. Aim 1 outcome variables will be obtained from Medical Records (attendance) and Provider Report (homework compliance). Aim 2 outcomes will be obtained from Baseline (week 0) and Posttreatment (16 weeks post-session 1) assessments of PTSD symptom severity, depression severity, quality of life, and relationship functioning. Aim 3 outcomes will be obtained from qualitative sources. Our Exploratory Aim outcomes will be obtained from Baseline, Posttreatment, and brief Weekly self-reports from Veterans and SPs. See below for measures.

5.5A.1 Aim 1. Aim 1 outcomes will be measured with methods drawn from Project HomeFront and our prior work coding session notes for PE/CPT treatment completion.⁵¹ PE attendance will be counted from review of Medical Records. Participants will have 'completed' PE when providers record they have successfully completed PE in a final session note. Providers will also be asked to log patient attendance and indicate the dates of attended sessions, missed sessions, and cancelled/rescheduled sessions. Homework compliance will be captured through patient observation by providers (Provider Report). Rating items were adapted from those used with Exposure and Response Prevention Therapy for Obsessive Compulsive Disorder (also a cognitive-behavioral exposure therapy).⁹³ Providers will also report on rates SP-provider contact weekly.

5.5A.2 Aim 2. Clinical outcomes for Aim 2 will be assessed through multiple forms (i.e., self-report and structured clinical interview), consistent with gold-standard methodology used in prior RCTs of PE and CPT. Baseline and posttreatment paper-and-pencil questionnaires will be completed by participants in both the RCT and IC phase of the study. Some participants in the IC phase will also receive structured interviews to allow the study team to implement all study procedures prior to beginning the RCT. IC participants will receive in-treatment assessments before sessions 2a and 2b to contribute to the intensive coaching and feedback providers receive for these early cases.

For RCT phase, structured clinical interviews will take place at Baseline (week 0) and posttest (within 4 weeks of final session). Self reports/surveys will take place at Baseline (during week 0) and at posttreatment (during final session). For drop out Veteran participants, posttest surveys will be completed 16 weeks post-session 1 and the posttreatment clinical assessment will be done within 4 weeks of that posttest survey. For late treatment completers (i.e., treatment takes more than 16 weeks), all posttest surveys and post clinical interviews will be delayed but will be done no later than 24 weeks post-session 1.

For the IC phase, weekly surveys will be given for the first 2 weeks of treatment (session 2a, and 2b). For the RCT phase, weekly surveys will be given during weeks 2, 4, 5, 6, 8, 10 and 12 of treatment. For participants, the weekly surveys during week 2 and 8 will be lengthier and more thorough. All structured interviews (CAPS-5³ and SCID-5-CT)¹² will be administered by trained and supervised assessors who are blinded to condition. Assessors will be trained and supervised weekly by [name], a licensed clinical psychologist with expertise in conducting structured diagnostic clinical interviews and assessing and intervening with patients experiencing mental health crises. For mailed assessments, we will use CCDOR's well-established modified-Dillman protocol with repeated mailings and an incentive (incentive schedule described below).⁶ For surveys of Veterans with PTSD, our team's response rates

have ranged from 55% to 85%. Given the short interval between assessments, we will include a telephone call reminder and an offer telephone administration to optimize response rates.⁶

5.5A.3 Exploratory Aim. Exploratory Aim outcomes (key social influences) will be measured from self-reports from both Veterans and SPs at Baseline, Posttreatment, and Weekly intervals. The frequency of measurement is necessary for examining the nature, shape, and change of key social influences week-by-week over the course of treatment. For the IC phase, the Weekly self-report for Veterans will be completed before each treatment session with a \$5 incentive for each form. IC phase participants will only receive these assessments for the first 3 weeks of treatment (session 2a and 2b). For the RCT phase, Veterans and SPs will be given surveys during weeks 2, 4, 5, 6, 8, 10 and 12 of treatment. Participants will be compensated \$10 for completing each survey during weeks 4, 5, 6, 10 and 12. The weekly surveys during week 2 and 8 will be lengthier and more thorough, thus participants will be paid \$20 for completing weekly surveys on those two weeks of treatment. Staff will make reminder calls to Veterans to ensure these weekly surveys are completed and offer telephone administration. SP data collection will take place by mail or online, because if SPs in standard PE receive assessments with Veterans at the medical center, we may unintentionally increase the rates of SPs reaching out to providers, artificially inflating family assistance within standard PE (i.e., cross-over effects). Veteran and SP participants are required to complete their baseline assessment survey before beginning treatment, as the baseline survey is part of study eligibility criteria. Participants will be given a \$40 incentive for the baseline surveys. Veteran and SP participant posttreatment assessments will be administered using CCDOR's modified-Dillman protocol, with a \$50 incentive for Posttest surveys, as well as a post-card reminder, second and third survey mailing package, telephone call reminders, and an offer of telephone administration to optimize response rates.⁶ For Weekly assessments, SPs from both conditions will receive a packet of self-report forms and postage paid envelopes at study enrollment (RCT only, these measures will be administered in person when SPs attend sessions in the IC phase). SPs will mail completed self-report forms to staff weekly and receive their incentive for each completed form. Study staff will make reminder calls each week to participants to complete the weekly survey. If study staff fail to reach a participant, another weekly survey will be sent along with a letter reminding him/her to complete the survey and mail back to the VA. For the few sessions that SPs in family supported PE attend, they will be offered in person administration of their weekly forms for convenience. We will also send Veterans and SPs a follow-up survey 3 months after the posttreatment assessment. Participants will receive a \$60 incentive for completing the 3 month follow-up survey, and we will use CCDOR's modified-Dillman protocol once again to optimize response rates. See attached Materials for study measures.

5.5A.4 Veteran/SP Measures. Unless otherwise specified, all measures have established reliability and validity (See Table 5). Aim 2: PTSD symptom severity will be assessed through Baseline, during treatment, and Posttreatment self-reports on the PTSD Checklist (PCL-5)² and Baseline and Posttreatment assessments using a structured clinical interview (CAPS-5; RCT only).³ Additional clinical outcomes will include depression severity (Patient Health Questionnaire; PHQ-9),¹³ quality of life (World Health Organization - Quality of Life, Brief; WHOQOL),⁹⁴ relationship functioning (Quality of Relationships Inventory, QRI),⁸⁹ and treatment satisfaction (Client Evaluation of Services Questionnaire, CSQ-8).⁹⁵ One defining principle of practical RCTs is prioritizing outcomes that are simple, clinically friendly, and typical of everyday good practice to improve the clinical relevance of findings.⁴ In typical VA practice, PE response is evaluated through repeated administration of the PCL⁵ or PCL-5,² which is simpler and quicker than a structured clinical interview. Consequently, PCL-5 scores will serve as our main

outcome for Aim 2. CAPS-5 (RCT only) scores will provide an important secondary outcome for formal diagnoses and facilitate comparison across trials.

5.5A.5 Exploratory Aim Outcomes: SPs' support for PE participation will be assessed using the Credibility/Expectancy Questionnaire, adapted for EBPs for PTSD (CEQ-PTSD)⁹⁶. SPs' symptom accommodation will be assessed through the Significant Others' Responses to Trauma Scale (SORTS).⁹⁷ SPs' behavioral support for treatment participation will be assessed through Veteran-report on the Support Checklist, developed during Project HomeFront ($\alpha = .78$; item-total correlations: 23-.70; significantly correlates with SP knowledge of and attitudes about treatment, SP contact with providers, social support, and symptom accommodation). Items assess SP behaviors in the past week that support or discourage PE attendance (e.g., help with homework).

5.5A.6 Covariates. SP support for PE may better influence adherence with less SP distress, less family conflict, greater provider-SP contact, and certain demographic characteristics (e.g., gender, age, or race/ethnicity). SP distress will be assessed using the PROMIS Perceived Stress scale⁹⁸ and General Functioning scale of Family Assessment Device (FAD). Frequency of provider-SP contact will be assessed in weekly provider reports. Demographic variables such as race, gender, SP-Veteran relationship (e.g., spouse, parent, adult child), and frequency of SP-Veteran contact will also be assessed at Baseline.

5.5A.7 Qualtrics Online Surveys

Survey administration format will transition to Qualtrics FedRAMP electronic survey software accessed via the VA cloud. This transition will support data collection during the current COVID 19 directives. Our study sites have been ordered to "shelter in place" during the pandemic, making paper survey mailings unachievable. Paper surveys will still be available to those who need or request them, but we plan to use online surveys as our primary modality.

Qualtrics FedRAMP has been approved for use from the VA OIT Security standpoint (Authority to Operate or ATO). The ATO status is currently approved for 1 year and a full 3-year ATO is in the works. Qualtrics FedRAMP surveys will contain a study ID number, time of data entry and limited individually identifiable information. Within the VA firewall, the study team at the VA will create a custom- built tracking app that will track each participant's enrollment and study status. Data will be routinely extracted from Qualtrics FedRAMP in the VA cloud and stored on secure CCDOR servers, using SQL database connections. All data will be stored and utilized within secure CCDOR servers that are part of the Minneapolis VAMC network and which operate behind the VA firewall. All data is tracked using a SQL database, with a GUI-front end system that restricts access to only those with approval to study data.

Qualtrics FedRAMP surveys will contain minimal individually identifying information. The only identifying information will be information that is self-reported by the participants (e.g. name, phone, email, which is best method of contact). No sensitive data will be stored outside of the VA protected environment. Once data are transferred for data analysis, data will be maintained on password-protected VA computers in the VA environment and on secure VA servers.

Study staff will monitor the functioning of the Qualtrics FedRAMP application. Only staff affiliated with this research protocol will have access to Qualtrics FedRAMP data collected for this study.

The PI or her designee will be responsible for monitoring data storage location and transfer of data between the VA cloud and VA server.

Participants will be sent their Qualtrics survey via a generic email to their personal email address, if the patient opts in for email usage. Prior to emailing participants, we will contact them by phone to ask permission to use their email for this purpose. If the participant does not opt in for email usage, they will be given the Qualtrics survey URL verbally over-the-phone or written on the recruitment and/or follow-up letters sent to them in the mail. Participants can complete hard copies of the survey by hand if they prefer.

All emails to participants will be extremely generic and will follow VA guidelines; they will not mention details of the study in the body of the email, participant names and PHI will not be used, and only generic secure hyperlinks (connected to Qualtrics) will be used.

Study providers will also use email to contact participants, when approved by their site, using their site's approved email protocol when patient's opt in for personal email usage.

Table 6. Implementation Framework Elements Guiding Process

Evaluation¹⁰⁰

Element	Key Question	Data Sources
Reach	
• Percentage approached who agree to participate?• Differences between participants and non-participants?• What influences willingness to participate?	
• Patient Screening Database• Process Log• Exit Interviews• SP self-reports
Effectiveness	
• What is the effect of the intervention?	
• Study outcomes• Exit Interviews• VA Interviews
Adoption	
• Greatest barriers to adoption?• Supports needed for clinics to adopt the intervention?	
• Process Log• VA Interviews
Implementation	
• What supports are needed to ensure consistent intervention delivery?• What tools are needed for consistent intervention delivery?	
• Process Log• VA Interviews• Fidelity Monitoring• Exit interviews• SP self-reports
Maintenance	
• What resources are needed to maintain the intervention?• What adaptations are needed to integrate into regular practice?	
• Process Log• VA Interviews• Fidelity Monitoring

Data collection is modeled after a prototypical Hybrid 1 study^{42,100} and will take place throughout the trial. Data sources include 1) study outcomes described above, 2) a Patient Screening Database, 3) a team observational Process Log for day-to-day observations,¹⁰⁰ 4) post-intervention interviews with providers and leadership (VA Interviews), 5) qualitative Exit Interviews with Veterans in partner supported PE, 6) Fidelity Monitoring, and 7) SP self-reports from Posttreatment. See Table 6.

[figure not shown]
5.5B. Qualitative Data Collection (Aim 3).

For Aim 3, we will examine the barriers/facilitators of real-world implementation and strategies to facilitate implementation through a mixed-method, multi-stakeholder process evaluation¹⁰⁰ with patients, providers, and mental health leadership. The RE-AIM framework will guide interview questions and assessments to evaluate Reach (factors influencing participation rate within target population), Effectiveness (impact of an intervention), Adoption (factors influencing if/how many VA hospitals would adopt the program), Implementation (factors influencing intervention integrity in real-world settings), and Maintenance (sustainability).¹⁰¹

The Patient Screening Database will reflect the number of participants screened and reasons for exclusion/inclusion. The Process Log will include observations and reflections on the team's daily experience with essential activities in implementing family supported PE within the trial. The Log allows for recording comments from clinical staff and patients not readily reported in formal data collection methods.¹⁰⁰ Qualitative open-ended interviews will be conducted with study providers and leadership at each site (i.e., study providers, team leaders, mental health leadership), upon completion of intervention delivery. Interviews will focus on relevant RE-AIM domains and implementing family supported PE with specific Veteran subgroups (i.e., women, racial/ethnic minorities, same sex couples). Brief semi-structured Posttreatment Exit Interviews with Veterans in family supported PE will assess 1) *reactions to the intervention, including experiences with trauma disclosure to SPs*, 2) how SPs influence Veterans personal treatment outcomes, and 3) recommendations for changes to improve the effectiveness of family engagement. Fidelity monitoring will evaluate the effectiveness of training, intervention integrity, and which intervention strategies proved particularly difficult/easy to master. SP self-reports and Veteran Exit Interviews will identify practical attendance barriers and solutions.

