active-listening, and role plays, using BFT approaches. Lastly, it will use tips from Motivational Interviewing for eliciting SP encouragement for PE participation, creating a tailored plan for SPs to support PE, and assisting SPs in follow-up telephone calls. The training team is highly seasoned in educating providers in these methods. The training will be video-taped for use in training future providers (e.g., due to provider attrition during the course of the study).

5.1C. Standard PE.

Providers will deliver PE consistent with the standard of care, with a flexible end date as they typically would in routine practice and will divide Session 2 into 2a and 2b. VA PE trainings encourage extending the therapy as needed, routinely resulting in a range of 8 to 15 sessions. Posttreatment assessments will be scheduled to coincide with when Veterans complete treatment to allow for this flexible end date. If participants are still in treatment at 16 weeks post-session 1, the posttreatment assessment will be delayed to allow them to get through as much of the treatment as possible prior to assessment. If the Veteran never attends session 1, their posttreatment will be scheduled 16 post-first missed appointment for session 1.

Family attendance will not be solicited by providers in standard PE. If a SP contacts a provider, the provider will proceed as he/she would in his/her routine practice, consistent with our design emphasis on real-world care. Quantity and quality of provider-SP contact will be measured by weekly provider report. We anticipate risk for cross-over effects from SPs reaching out to providers is minimal as considerable effort is required by SPs to gain access to Veterans' providers (i.e., Veterans must request and sign a Release of Information). Additionally, while we did not capture who initiated the provider-SP contacts reported among 17% of SPs within Project HomeFront, qualitative interviews suggest these contacts are typically initiated by providers. In qualitative interviews, SPs were enthusiastic about being involved in Veterans' care, but few SPs had considered reaching out to Veterans' providers.

Table 2. Content Added for Family Supported PE	
PE#	Task
1	
 • Eliciting benefits of further SP attendance • Brief discussion of how SPs can help in PE
2a	
 • Brainstorm how SPs encourage/discourage PE adherence and approaching trauma-reminders

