2b	
 • Develop SP's plan for supporting adherence • Anticipate barriers to success; role play solutions
3, 5	
 • SP telephone check-ins for trouble-shooting support plan with longer in-person check-ins when indicated

5.1D. Family Supported PE (Table 2).

Providers will deliver the 10 session PE protocol as they typically would with additional material outlined session by session below. As discussed above, they will divide session 2 into 2a and 2b (11 total sessions delivered over an 11-16 week period). If the dyad is randomized to include their family in treatment sessions, SPs will attend the first session with the Veteran and be encouraged to attend both

session 2a and 2b (see Table 2). Each session attended by a family member will include the following content. We will ask Veterans in self-reports prior to session 1 about their preference for having their SP present for their Session 1 trauma discussion with their providers (i.e., trauma interview). This preference will be honored to promote early retention and keep the intervention Veteran-centered.

Session 1: The last twenty minutes of Session 1 will involve a) eliciting how further SP attendance could be of benefit the dyad, using Motivational Interviewing tips, b) discussion of how the SP can support PE participation should this be the only family session, c) and discussion of the benefits of talking further about trauma with loved ones, using Motivational Interviewing strategies.

Session 2a: We will devote fifteen minutes to discussing how SPs naturally encourage or discourage Veterans to approach trauma reminders and participate in treatment. Session 2b: Thirty minutes will be devoted to a) create a tailored plan for SPs to support Veterans' PE participation, including planning trauma disclosure to family when indicated or desired and b) problem-solving barriers to the success of the SPs' support plan.

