Providers will deliver the 10 session PE protocol as they typically would and will divide session 2 into 2a and 2b (11 total sessions delivered over an 11-16 week period). If the dyad is randomized to include their family in treatment sessions, SPs will attend the first session with the Veteran (up to session 3), two 15 minute telephone check-ins with providers. If telephone check-ins reveal a) that the family support plan is not going well, b) unresolved ambivalence about the treatment, or c) preferences for greater assistance to the SP in how to support the Veteran's care, the provider can elect to add dyadic session(s) to discuss these issues, consistent with how this intervention is likely to be delivered in real-world care if their 15 minute check-ins prove insufficient. These sessions will discuss progress and the support plan using skills from prior sessions. Dyads expressing additional family needs or support for SPs' mental health will be provided site-specific referrals, including services for SPs, children, parent skills training, and family or couple counseling as indicated. Study assessments are described below under 'Data Sources.'

Providers

Providers will be members of the research team and included in the IRB as study staff (to be added in future amendments). After providers have completed their role in delivering the treatment, they will be invited to participate in semi-structured interviews conducted via telephone for Secondary Aim 2 (process evaluation). Therapist interviews will last approximately 50 minutes and leadership interviews will last approximately 30 minutes. The interviews will be recorded, transcribed, and coded. Therapist interviews will last approximately 50 minutes. The interviews will be recorded, transcribed, and coded.

Mental Health Leadership

Two members of mental health leadership at each site will be invited to participate in semi-structured interviews conducted via telephone for Secondary Aim 2 (process evaluation). and leadership interviews will last approximately 30 minutes. The interviews will be recorded, transcribed, and coded.

5.1I.2. Data Sources. Sources of data are depicted in Table 3.

Veterans and SPs

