5.6B2. Aims 1 and 2. After completing the above steps, we will test our hypothesis for Aim 1 using generalized linear mixed models. The number of sessions attended, within the assumed and appropriate fitted distribution, will be modeled with treatment and site as fixed effects and a random provider effect (clustering by provider). Analyses for Aim 2 will similarly use mixed models to examine differences between conditions on PCL-5 scores over time, modeling the treatment, time, and treatment by time effects. Secondary analyses will examine CAPS-5 scores and loss of diagnosis on the CAPS-5 (both PTSD diagnosis and subclinical PTSD diagnosis) to facilitate comparisons with existing and ongoing research on treatments for PTSD. We will also examine differences between conditions on PHQ-9, WHO-QOL, QRI, and CSQ-8 scores.

Analyses will follow the same general approach as Aim 1, with some exceptions. First, some indices are dichotomous (i.e., presence or absence of PTSD or subclinical PTSD diagnosis). Models will be fit using appropriate distribution and link functions (i.e. for binomial distribution and logit links for PTSD diagnosis; whereas mean group differences might fit a normal distribution). Second, unlike Aim 1, which relies on administrative data, Aim 2 outcomes rely on

self-report data, where some attrition is inevitable. Analyses will include examining group differences using available data, as well as analyses employing imputation as described above. To study the time-dependence of clinical outcomes, we will model the first-order transition probabilities of Markov chains (under treatment and control) with auto regressive random intercepts, random slope (provider), and fixed effects for treatment, site, sessions attended, and homework compliance. Lastly, we will explore indirect pathways from family supported PE to improved treatment outcomes through greater adherence (e.g., treatment condition → session attendance → PTSD symptoms), using approaches for testing indirect effects described below.

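### Is the primary session count undermined because the course is written as 8 to 15 sessions in one section and 11 in two others?

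*Combined protocol and SAP*

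**What the plan says.** Section 5.6A names session attendance as the primary outcome. Section 5.5A.1 gives its source: "PE attendance will be counted from review of Medical Records". It adds that "Aim 1 outcomes will be measured with methods drawn from Project HomeFront and our prior work coding session notes for PE/CPT treatment completion". Providers also log the dates of attended, missed and cancelled sessions, and completion is whatever the provider records in a final note, with no session number attached. Section 5.6B2 sets the model: "The number of sessions attended, within the assumed and appropriate fitted distribution, will be modeled with treatment and site as fixed effects", plus a random provider effect.

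Course length appears in three places:

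- **5.1C, standard PE.** Treatment is delivered "with a flexible end date as they typically would in routine practice". The text continues: "VA PE trainings encourage extending the therapy as needed, routinely resulting in a range of 8 to 15 sessions".
- **5.1D, family supported PE.** Of the providers it says: "they will divide session 2 into 2a and 2b (11 total sessions delivered over an 11-16 week period").
- **5.1I.1, overview of the RCT phase.** "Providers will deliver the 10 session PE protocol as they typically would and will divide session 2 into 2a and 2b", again 11 in total. This comes before the sentence on dyads randomized to family involvement.

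Section 5.5A.2 adds a timing rule without naming an arm: "For late treatment completers (i.e., treatment takes more than 16 weeks), all posttest surveys and post clinical interviews will be delayed". Sections 5.1D and 5.1I.1 let providers add dyadic sessions in the family arm. Sections 2.2B and 2.2C and Table 2 call the same contacts check-ins. No section says whether they count as attended sessions.

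**The concern.** A raw count compares adherence fairly only if the arms have similar numbers of sessions to attend. Read literally, arm by arm, the plan seems to allow up to 15 sessions in standard PE and 11 in family supported PE. A Veteran who attended every session of a 13-session standard course would score 13, and one who attended all of family supported PE would score 11. Both adhered fully, yet they differ by 2 sessions, which is the effect the trial is powered to detect. Planned course length would then be part of the treatment contrast, and the primary result could not be read as adherence alone. The optional dyadic visits raise a smaller version of the same question in the opposite direction.

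**Working it through.** **1. The plan's own figure.** Inputs from 5.6A1: SD 4.45, 78 per arm, difference 2 sessions. Two-sided alpha of 0.05 is assumed, since 5.6A1 states none.

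- SE = 4.45 × √(2/78) = 0.713
- Power = Φ(2/0.713 − 1.96) = 80.1%, matching the stated 80%

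This calculation does not depend on a maximum session count.

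**2. Size of the problem if each section governs its own arm.** Let c be the proportion completing and m the mean number of sessions among standard-arm completers. Family-arm completers attend 11, and dropouts behave alike in both arms. The shift in the difference (family minus standard) is c × (11 − m). Section 2.0 puts dropout near 35%, so c = 0.65; c = 0.50 is an assumed lower value. The documents give no mean for completers; the midpoint of 8 to 15 is m = 11.5.

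| c | Shift | Share of the 2-session target | Power at a true +2 | Two-sided error | Part of the error favouring family PE |
|---|---|---|---|---|---|
| 0.50 | 0.50 × (−0.5) = −0.25 | 12.5% | Φ(1.75/0.713 − 1.96) = 69% | 6.4% | 1.0% |
| 0.65 | 0.65 × (−0.5) = −0.325 | 16% | Φ(1.675/0.713 − 1.96) = 65% | 7.4% | 0.8% |

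The last column is Φ(−1.96 + shift/SE). It is below the nominal 2.5%, so at this midpoint the excess error runs against the new treatment and produces no false claim for it.

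**3. Size under one common course.** If completers in both arms average the same length, whatever it is, the shift is c × 0 = 0.

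**4. Which reading the text supports.**

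- 5.1I.1 gives 11 sessions for RCT participants before it turns to the family arm, so 11 is not written as a cap on that arm.
- 5.1C, 5.1D and 5.1I.1 all defer to how providers usually work, and 5.1C ties that to the flexible end date.
- The late-completer rule in 5.5A.2 applies to everyone.
- 5.1A has the same providers deliver both arms, with randomization blocked within provider. Different length rules by arm would be a notable design feature, and none is described.
- In 5.1C, 8 to 15 describes what routine extension leads to. In 5.1D and 5.1I.1, 11 is the 10-session manual with session 2 split. A descriptive range and a nominal length can both hold for one course.

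**5. Do the planning figures rule out an 11-session count?** On a 0 to 11 scale, the largest SD at the stated mean of 7.30 is √(7.30 × 3.70) = 5.20, above 4.45, so the stated pair fits. A conflict appears only if the 2-session gain is added and the SD held: at 9.30 the limit is √(9.30 × 1.70) = 3.98. Holding the SD constant is an ordinary planning convention, and a smaller true SD would raise power.

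**6. Dyadic add-ons.** If they are not counted, the shift is zero. If they were, an assumed mean of 0.1 to 0.2 per family-arm Veteran gives a two-sided error of 5.2% to 5.9%.

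**The case for a change.** The strongest case is that the sections do not agree as written. 5.1C and 5.1I.1 differ about the standard arm itself, so the discrepancy does not depend on reading the sections arm by arm. The 11 to 16 week period in 5.1D reads as more fixed than the open-ended wording of 5.1C. Nothing in 5.5A.1 or 5.6B2 settles which sessions count, and the 6-week break rule in 5.1F limits time, not number. The arm-specific effect could also be larger or reversed. If standard-arm completers averaged 10, the shift would be +0.50 to +0.65 session toward family supported PE, with two-sided error of 10.8% to 14.9% by the normal approximation. In a simulation with dropouts spread over 0 to 7 sessions and the SD left to follow from the model, it was 12.3% to 19.2%. Writing down a counting rule costs one sentence.

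The wording discrepancy stands, and so does the silence on extension and add-on sessions. The error figures do not carry over, because every one of them needs different course lengths in the two arms, and the averages of 10 or 12 that give the large values are not in the documents.

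The obvious remedy would also gain little. A rule that counts PE sessions, extensions included, the same way in both arms is what someone coding the charts would do anyway. If the course lengths really differed by arm, that rule would leave the difference in the primary count. Truncating at 11 as a sensitivity analysis would not change the primary result and would not touch courses that end early.

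**Conclusion.** The concern does not call for a change to the plan. The best-supported reading is one common course, delivered flexibly by the same providers in both arms, and under it the bias in the primary count is zero. The arm-specific reading would shift the difference by 0.25 to 0.33 session at the midpoint of the documented range, assuming 50% to 65% completion, but the text gives that reading little support. The stated mean and SD are compatible with either course length, and the power figure reproduces at 80.1%.

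A flexible end date does mean that a session count mixes adherence with course length. That is a fair trade-off in a practical trial. Completion is recorded separately from the provider's note, and the logged session dates allow sessions per completer to be described by arm without any new provision.

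What remains is editorial. The session wording in 5.1C, 5.1D and 5.1I.1 must be reconciled, and this review does not say which length is right. Analysts can be expected to count PE sessions alike in both arms and to keep dyadic check-ins apart, as the term PE attendance and the separate tracking of provider contact with support persons already suggest. The conclusion rests on course length not being set differently by arm in practice.
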